**LIST OF ABBREVIATIONS**

HPV	Human Papilloma Virus
Hr-HPV	High-risk Human Papilloma Virus
ART	Antiretroviral therapy
HIV	Human Immunodeficiency Virus
PaHIV	Perinatally acquired HIV
WLWH	Women living with HIV
CIN	Cervical Intraepithelial Neoplasia
VIA	Visual Inspection with Acetic acid
BHIVA	British HIV Association
HYPNet	HIV in Young People Network
NSC	National Screening Committee
NHS	National Health Service
PHE	Public Health England
WHO	World Health Organisation
NHSCSP	NHS Cervical Screening Programme
PCR	Polymerase Chain Reaction
GCP	Good Clinical Practice
IEC	Independent ethics committee
IRB	Institutional Review Board
PI	Primary investigator
REC	Research Ethics Committee

## 1. TRIAL SUMMARY

**Title:** Screening for HPV and cervical cancer in young women with perinatally acquired HIV (SHiP study)

**Summary:** This protocol describes an observational study of cervical cytology assessment, high risk human papilloma virus (hr-HPV) status, and HPV antibody titres amongst adult women living with perinatally acquired HIV infection (PaHIV). Eligible consenting participants will have two samples taken; firstly, a cervical sample tested for cytology and Hr-HPV with the Cepheid GeneXpert HPV; secondly, Blood sampling, serum will be assessed for hr-HPV serology. All women with PaHIV, vaccinated and unvaccinated for HPV, over the age of 18 years will be eligible and will be recruited into one of two cohorts: (1) sexually active women: full study, cervical and blood sampling (n=50) or (2) non-sexually active women, blood sampling only (n=30). Follow up for abnormal smear results or hr-HPV positivity will be arranged through standard NHS referral pathways for colposcopy.

**Rationale:** HIV increases the risk of HPV related cervical intraepithelial neoplasia (CIN) and cervical cancer, and it is hypothesized that women with perinatally acquired HIV may be more at risk from an earlier age than the general population, and than women living with HIV acquired in adulthood, although there is little data to support this. For this reason, the HIV in Young People Network (HYPNet) guidelines state that cervical screening should start when a young woman with PaHIV becomes sexually active, irrespective of age(1), but despite these recommendations this is not included in UK guidelines. Currently cervical cytology is routinely available for all women with HIV yearly from the age of 25 to 65 in England, but younger women (<25 years) with PaHIV are not currently eligible for NHS cervical screening.

We hypothesise that young women with PaHIV may benefit from cervical screening < 25 years of age, due to an increased risk of cervical abnormalities as a consequence of lifelong impaired immune function and the potential for suboptimal responses to the HPV vaccination. A delay in screening until aged 25 may miss early detection of manageable pre-cancers and cancer.

**Primary aim:** To identify the prevalence of abnormal cervical cytology in a cohort of sexually active young women with PaHIV aged  $\geq 18$  years

**Secondary aims:**

- To identify the prevalence of high-risk HPV by subtype in a cohort of sexually active women with PaHIV aged  $\geq 18$  years
- To identify the prevalence of CIN2+ in a cohort of sexually active women with PaHIV aged  $\geq 18$  years
- Explore the use of HPV testing as a primary screening tool compared with cervical cytology in this cohort
- Characterisation of immunological and other correlates with high-risk HPV carriage, cervical abnormalities and CIN2+
- Investigate antibody titres to the HPV in vaccinated and unvaccinated women and compare this to the antibody responses to other vaccinations (e.g. hepatitis B)

- Explore the relationship between HPV-antibody titres and current immune function (CD4 count) and CD4 count at the time of vaccination
- Explore the uptake and acceptability of cervical screening before the age of 25 in this cohort
- Explore the cost-benefit of providing cervical screening before the age of 25 in this cohort

**Planned sample size:** 80

## 2. STUDY BACKGROUND

Cervical cancer is caused by high-risk HPV subtypes, and the relationship between HIV and HPV is well recognised. In HIV uninfected women HPV 16 and HPV 18 are responsible for 71% of cervical cancers(2). Women living with HIV are more likely to have persistent HPV infections, and are at greater risk of developing complications secondary to this, including cervical dyskaryosis, intraepithelial neoplasia (CIN) and cervical cancer(3–6). It is due to these higher rates as well as the more rapid progression of disease that BHIVA recommends annual smear tests for HIV positive women aged 25-65 years(7), compared to 3-yearly for HIV non-infected women. BHIVA has no specific guidance for women with perinatally acquired HIV (PaHIV) under 25 years due to a paucity of data, but the HIV in Young People Network (HYPNet) state that cervical screening should start within a year of when a young woman with PaHIV becomes sexually active, ideally with baseline colposcopy(1). Due to limitations of national testing policies within the UK this is no longer achieved for those under 25.

Although there are very little data on cervical screening in people with PaHIV, this population is known to be at an increased risk of all cause malignancy, with more than half being associated with chronic oncogenic viral infections(8). It is proposed that the pathogenesis of HPV related disease may be altered in those with PaHIV due to living with the HIV virus throughout childhood and sometimes having significant immunosuppression during this time. Moscicki et al. found that adolescents with primarily horizontally acquired HIV had a much higher rate of high grade squamous intraepithelial lesions (HSIL) at 22% compared with 5% in age- and risk-matched controls(9). In the same cohort, 77% of those with HIV were positive for HPV, and only 30% of these had normal cytology, compared to 55% testing positive for HPV in the HIV-negative controls, of which 70% had normal cytology(10). Brogly et al. also found a higher prevalence (48%) of cervical abnormalities in those with PaHIV who had a smear test compared to that documented in aged matched HIV-negative adolescents(11). In a study looking at HPV infections in non-sexually active PaHIV, 30% of girls had anogenital HPV compared to 7% of HIV-exposed but uninfected girls, although the HIV uninfected girls were significantly younger in age. They suggest that HPV may be commonly acquired non-sexually in PaHIV, and that vaccine efficacy may be different in this group(12). Within our cohort of young adults with PaHIV (the 900 clinic) at Imperial College Healthcare NHS Trust, previous data showed 17% of young women had an abnormal first smear, with a median age of 19 years, and a median coitarche-first smear interval of 2 years. Overall the median age at coitarche was 16 years(13).

In the NHS cervical screening programme, samples are not routinely tested for HPV unless there are borderline or low-grade changes. In 2016, the UK National Screening Committee (NSC) recommended that hr-HPV testing should replace cervical cytology as the primary cervical screening method. NHS England plans to achieve full rollout of this by the end of 2019, and this is already being implemented in some pilot sites across England. Women living with HIV (WLWH) will continue to have annual screening using primary hr-HPV testing rather than cytology(15). Women who are positive for hr-HPV will also have cervical cytology sent to triage whether they should be referred for colposcopy or have repeat screening in one year(15).

Other international guidelines recommend primary cervical screening with hr-HPV(16), and management protocols differ slightly on the referral pathway to colposcopy, with some recommending partial genotyping and direct referral to colposcopy for women testing positive for the highest risk HPV (16 or 18)(17). In our cohort, there is little evidence to determine the best cervical screening algorithm, so for this reason we have elected to offer colposcopy to all women testing positive for hr-HPV as well as those with abnormal cervical cytology.

The GeneXpert HPV Assay (Cepheid, Sunnydale, California, USA) is a clinically validated real-time polymerase chain reaction (PCR) assay, which uses a single-use cartridge for the detection of 14 types of hr-HPV in 3 channels (HPV 16, HPV 18/45, and other hr-HPV 31/33/35/52/58/51/59/39/56/66/68)(18). The NHS Cervical Screening Programme (NHSCSP) lists the Cepheid GeneXpert as acceptable for use within screening for HPV triage and test of cure(19).

Part of the reason for this move to primary screening with HPV in the UK is due to the introduction of the national HPV immunisation programme in 2008. It is thought that the hr-HPV testing is a more appropriate screening method in HPV vaccinated women, as the incidence of CIN should be lower(15). Since 2008, HPV vaccination has been offered to all girls aged 12-13 years (with a catch up programme for the first two years in girls aged up to 18 years). Until 2012, girls were offered the bivalent vaccine (against HPV 16 and 18), and since then the quadrivalent vaccine has been offered (HPV 16, 18, 6 and 11)(20). Studies looking at immunogenicity of the HPV vaccine have showed overall good responses in people living with HIV, with better and more sustained responses in those with a higher CD4 count and undetectable viral load(21-24), although data in people with PaHIV is sparse. A study by Giacomet et al. looked at HPV vaccine safety and response in HIV-infected and -uninfected adolescents in Italy(21). They recruited 46 females and males with HIV aged 13-27 years, and an equal number of age matched controls; the mean CD4 count in this group was 715 cells/ul and 95% had an undetectable viral load at baseline. At one month post vaccine, seroconversion rate was 85% in the HIV positive group compared to 91% in the control group. The mean titres measured using a HPV IgG ELISA kit were 5.8ug/ml less in the HIV positive group at 18 months post vaccine(21). In another study looking at vaccine response by Kahn et al. 99 women with HIV (none perinatally acquired) were recruited, 69 into a non-antiretroviral therapy (ART) group, and 30 into an ART group(22). Overall mean CD4 count was 613 cells/ul, with 86% having a  $CD4 \geq 350$  cells/ul. They found that geometric mean titres (GMT) were around twice as high in the ART group compared to non-ART group, and this was statistically significant for HPV types 16 and 18. They found that GMT was also significantly lower in the non-ART group versus a historical comparison group. Seroconversion rates were 100% for all four HPV types in the ART group but were as low as 92.3% for HPV 18 in the non-ART group and this dropped significantly by week 48 to 67.6%. Titres were also higher at week 28 and 48 in those with  $VL < 400$  copies/ml, but this was only significant for HPV 11(22). Lastly, in a study looking at HPV vaccine responses in children with HIV aged 7-12, seroconversion rates were 96% but immune titres to HPV 6 and 18 were 30-60% lower than those achieved in historical controls(25). The clinical significance of this is unclear, and further studies are needed to assess the long-term efficacy of the HPV vaccination in young people living with HIV.

### 3. STUDY OBJECTIVES

**Primary objective:** To identify the prevalence of abnormal cervical cytology in a cohort of sexually active young women with PaHIV aged  $\geq 18$  years

**Secondary objectives:**

- To identify the prevalence of high-risk HPV by subtype in a cohort of sexually active women with PaHIV aged  $\geq 18$  years
- To identify the prevalence of CIN2+ in a cohort of sexually active women with PaHIV aged  $\geq 18$  years
- Explore the use of HPV testing as a primary screening tool compared with cervical cytology in this cohort
- Characterisation of immunological and other correlates with high-risk HPV carriage, cervical abnormalities and CIN2+
- Investigate antibody titres to the HPV in vaccinated and unvaccinated women and compare this to responses to other vaccinations (e.g. hepatitis B)
- Explore the relationship between HPV-antibody titres and current immune function (CD4 count) and CD4 count at the time of vaccination
- Explore the uptake and acceptability of cervical screening before the age of 25 in this cohort
- Explore the cost-benefit of providing cervical screening before the age of 25 in this cohort

### 4. STUDY DESIGN

This is an observational study of cervical cytology and hr-HPV carriage in young females attending a large tertiary referral centre providing HIV care for perinatally acquired HIV infection (n=80). Recruitment will be over 18 months from the study start date or until the planned sample size is recruited. Consenting study participants will give consent to access HPV vaccination history from GP records with the dates and vaccines received.

Eligible young women ( $\geq 18$  years with PaHIV infection) will be invited to join the study. They will be given time to read the patient information sheet and written informed consent will be taken by a study team member. Women will be recruited into one of two cohorts: (Cohort 1) Aged  $\geq 18$  and sexually active, (Cohort 2) Aged  $\geq 18$  and not sexually active.

At enrolment, a single study visit will be required for both cohorts, during which, a venous blood draw of 6mls will be taken plus an optional additional 30mls (36mls total) and an optional urine sample for the Biobank. Participants will be asked to complete a short 1-page questionnaire and a data collection sheet will be completed by study staff. Women enrolled into cohort 1 will also have a speculum examination and a cervical sample will be tested for hr-HPV using the Cepheid GeneXpert HPV and sent for cytology in routine NHS laboratories.

Results of cervical cytology and cervical hr-HPV testing will be given to the study participants in cohort 1. This will either be at an arranged second visit, or via a phone consultation, email or letter depending on the preferences of the individual. Referral to colposcopy services will be made in accordance with current national clinical pathways for any young woman with

abnormal cytology results. In the case of normal cytology in the presence of hr-HPV, these women will also be referred for colposcopic examination. The blood HPV serology are for research purposes only and hence individual results will not be given back to the study participants. At the end of the study, aggregate results will be shared with the study participants.

The HPV vaccination is now available to all women in the UK aged less than 25 years. If women have not been vaccinated at the time of enrolment but are subsequently vaccinated, we will consent them for repeat serological testing at the next clinic appointment following the completion of the HPV vaccine course.

## 5. PARTICIPANT ENTRY

### 5.1 Screening

Young adults living with perinatally acquired HIV-1 attending the 900 clinic at Imperial College Healthcare NHS Trust London, or the Team clinic at the Mortimer Market Centre, aged 18 years and older.

### 5.2 Inclusion criteria

- Cohort 1:
  - PaHIV females age 18 years and older
  - Sexually active
  - Able to give informed consent
- Cohort 2:
  - PaHIV females age 18 years and older
  - Able to give informed consent

### 5.3 Exclusion criteria

- Cohort 1:
  - Pregnancy
  - Not sexually active
  - Previous total abdominal hysterectomy
  - Unable to give informed consent
- Cohort 2:
  - Unable to give informed consent

### 5.4 Withdrawal criteria

Each participant has the right to withdraw from the study at any time. In addition, the Investigator may discontinue a participant from the study at any time if the Investigator considers it necessary for any reason.

Participants who withdraw from the study will have their censored data included in the study analysis unless specifically requested by the individual not to include it. Any stored

samples remaining on withdrawn participants will be either destroyed or remain within the laboratory for future testing depending on the participant's wishes.

The reason for withdrawal will be recorded in the CRF.

## 6. STUDY PLAN

### 6.1 Visit summary

The study will consist of one visit, plus an optional second visit, and where possible these will coincide with routine clinical visits:

- Screening, patient information and consent
- Study visit 1 (may be at the same time as screening, provided sufficient time has been given to read the patient information sheet and understand the study) – all participants
- Study visit 2, results – optional for cohort 1

**6.2 Screening visit:** Patients will be assessed against the above inclusion and exclusion criteria and will be asked if they wish to participate if they are eligible for the study.

To all eligible individuals, an explanation of the study will be provided along with a copy of the participant information sheet. They will be given as much time as they need to consider their participation and will be informed that participation is voluntary and a decision not to participate will not affect their clinical care. The participant must personally sign and date the latest approved version of the Informed Consent form before any study specific procedures are performed, in the presence of a study team member.

Written and verbal versions of the Participant Information and Informed Consent will be given to participants detailing no less than: the exact nature of the study; what it will involve for the participant; the implications and constraints of the protocol, and any risks involved in taking part. It will be clearly stated that the participant is free to withdraw from the study at any time for any reason without prejudice to future care, and with no obligation to give the reason for withdrawal.

Optional sub-study: Consent for an additional donation of blood and urine sampling to the Biobank for future research is optional and consent for the use of any remaining blood samples taken as part of this protocol for use in future research into the immune system and viral infections as part of the Communicable Diseases Research Biobank will also be obtained.

The participant will be allowed as much time as wished to consider the information, and the opportunity to question the Investigator, their GP or other independent parties to decide whether they will participate. Written Informed Consent will then be obtained and a copy of the signed Informed Consent will be offered to the participant. The original signed form will be retained.

Visit 1 will either be at the time of the screening visit, their next routine clinic visit or as an additional study visit depending on participant preferences.

**6.3 Visit 1:** At visit 1 (either the same day as study enrolment or scheduled to another date as per participant preference) each participant will have their eligibility and consent in the trial confirmed. Clinical and demographic information will be recorded on the study CRF and will include:

- Age
- Ethnicity
- Current CD4 count
- Current CD4:CD8 ratio
- Current HIV-1 RNA viral load
- Nadir CD4 count
- Length of viral suppression <50 copies/ml
- Current antiretroviral therapy
- Concomitant medications
- Smoking
- Menarche
- Coitarche
- Obstetric history
- Gynaecology history including previous smear results
- Contraception
- HPV vaccination history (including age at vaccination, type, number of doses)
- Other vaccination history
- CD4 count at time of first HPV vaccination (if known)
- Lifetime number of sexual partners
- Diagnosed STIs
- History of genital warts
- Consent to access GP records for HPV vaccination details where GP aware of status

[figure not shown]
Investigations:

- Cervical smear test
- Cervical sampling for hr-HPV testing
- Blood for serology
- Optional Blood and urine for Biobank

**6.4 Visit 2 (optional for cohort 1, 2-4 weeks later):** Attendance for results of the cervical cytology and hr-HPV will be made with the research team. If a participant does not wish to attend for a second visit they will be given the option to get their results by phone, letter or email. All other tests are considered research tests and the individual results will not be given back to the study participant. Any abnormal cervical cytology result will be referred to local colposcopy services in accordance with local and British guidelines. Women who test positive for any hr-HPV will also be referred to colposcopy for the purposes of this study. Consent will be sought to collect outcome data following gynaecology referral.

**6.5 Visit 3:** For those women who receive HPV vaccination after enrolment into the study, repeat blood tests will be taken at the next clinic visit after completion of the vaccine course.

The study procedures algorithm can be seen in Figure 1.

**Figure 1: Management protocol for participants**

## 7. STUDY PROCEDURES

### 7.1 Cervical sampling for smear test and hr-HPV testing

Cervical cytology will be performed by a trained healthcare professional in accordance with current guidance in England for liquid based cytology using a disposable plastic speculum for speculum examination. A 1ml aliquot will be analysed for hr-HPV using the Cepheid GeneXpert HPV.

The risks to the participant of the procedure are discomfort and vaginal bleeding after the procedure. The participant may also feel discomfort vaginally following the speculum examination.

### 7.2 Venepuncture and urine

Participants will be consented to donate 6mls for serological testing, and an optional additional 30 mls of blood and a urine sample to be stored in the Biobank at Imperial College. This will be used for additional research testing for future viral and immune studies. Where possible blood taking will coincide with routine clinical monitoring blood taking.

The risks to the participant of venepuncture are pain and bruising following the procedure. The participant may also feel faint due to a vaso-vagal response or hypotension, and in this case the venepuncture will cease and the patient will be laid flat until recovery.

HPV antibody serology: 1 x Red top 6 mls

BioBank EDTA: 5 x purple top 6ml to 30 mls

Total samples at Visit 1:

- \* Blood: One 6ml Red top tube: 6ml
- \* Blood: (sub-study) Five 6ml EDTA samples for research: 30 mls
- \* Smear test and HPV testing: One liquid based cervical cytology
- \* Urine: (sub-study) One universal container

Total samples at Visit 3 (if applicable):

- \* Blood: One 6ml Red top tube: 6ml
- \* Blood: (sub-study) Five 6ml EDTA samples for research: 30 mls

All samples will be sent under the unique study number: cohort 1: SHiP/1/000/0, cohort 2: SHiP/2/000/0

## 8. DEFINITION OF END OF PROGRAMME

The end of the study is the date of final follow up of the final participant be that colposcopy or final smear results visit. The final results of the study will be shared with all participants as a letter and information sheet with explanation. A specific results-sharing participant meeting will be organised to allow further study results to be explained as required.

## 9. STATISTICAL ANALYSIS

- **Summarising data:** Characteristics of the study population will be described using mean and standard deviation, median and interquartile range, or number and percentage as appropriate. This information will also be stratified by age group.
- **Primary outcome:** The prevalence of cervical abnormalities within the cohort and by age group (18-24 and  $\geq 25$ ) will be calculated
- **Secondary outcomes:**
  - The prevalence of hr-HPV by type in young women with PaHIV will be calculated and stratified by age group
  - The prevalence of CIN2+ in young women with PaHIV will be calculated and stratified by age group
  - Comparison of HPV positivity with cervical abnormalities in young women with PaHIV
  - Characterisation of immunological and other correlates with hr-HPV carriage, cervical cytology results, CIN2+ and HPV type-specific antibody titres using the appropriate statistical test (Pearson's chi squared, Fisher's exact, Wilcoxon rank sum)
  - A measurement of HPV type-specific antibody titres in HPV vaccinated and unvaccinated young women with PaHIV, and a comparison with e.g. antibody titres to hepatitis B vaccination
  - Correlations of HPV-antibody titres and current immune function (CD4 count) and CD4 count at the time of vaccination
  - Acceptability will be assessed by the proportion of women who are offered enhanced cervical screening but decline.
  - Cost effectiveness will be assessed by evaluating the yield of abnormal results (cytology and hr-HPV) versus the cost of the tests

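### Section 9 describes HPV antibody titres by vaccination status only and does not separate the sexually active from the non-sexually active cohort, so antibody from infection and from vaccine is mixed

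*Combined protocol and SAP*

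**What the plan says.** Both cohorts give blood for HPV serology. Under the Trial Summary and Section 4, Cohort 1 (50 sexually active women) also gives a cervical sample, while Cohort 2 (30 women who are not sexually active) gives blood only. Serology is therefore the only study test that Cohort 2 can inform.

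The objective in Section 3 is "Investigate antibody titres to the HPV in vaccinated and unvaccinated women and compare this to responses to other vaccinations". The matching item in Section 9 is "A measurement of HPV type-specific antibody titres in HPV vaccinated and unvaccinated young women with PaHIV", followed by "and a comparison with e.g. antibody titres to hepatitis B vaccination". A separate item plans "Characterisation of immunological and other correlates with hr-HPV carriage, cervical cytology results, CIN2+ and HPV type-specific antibody titres using the appropriate statistical test" and names chi-squared, Fisher's exact and Wilcoxon rank sum tests.

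The only stratifier named in Section 9 is age group. It is attached to the population characteristics ("This information will also be stratified by age group"), the primary outcome, hr-HPV prevalence and CIN2+, but not to the titres. Neither cohort nor sexual activity is mentioned in Section 9. Section 6.5 adds a repeat blood sample (Visit 3) for women vaccinated after enrolment; Section 9 does not say how it will be used.

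**The concern.** The Trial Summary gives possible suboptimal response to HPV vaccination as part of the rationale, and Section 3 sets HPV titres beside responses to other vaccines. The titres are thus meant to inform vaccine response. In an unvaccinated sexually active woman, however, antibody may come from infection, and in a vaccinated one from either source. Infection-derived antibody can then hide a poor vaccine response. The planned correlations of titre with CD4 count inherit the same ambiguity.

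The design already contains a split that would help, namely the two cohorts, but Section 9 gives it no role. Section 2 also reports, of a study in non-sexually active girls with PaHIV: "They suggest that HPV may be commonly acquired non-sexually in PaHIV, and that vaccine efficacy may be different in this group". Unvaccinated Cohort 2 women bear on that question, yet no analysis reports them separately.

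**Working it through.** **1. The plan's own figure.** 50 + 30 = 80, which agrees with the planned sample size. Cohort 1 would supply 50/80 = 62.5% of enrolment serology. The documents give no alpha, power, titre SD or coverage by cohort, so nothing further can be reproduced. Steps 2 to 4 rest on assumptions.

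**2. Confounding of an unstratified mean titre difference.** Let D be the mean titre difference, Cohort 1 minus Cohort 2, at equal vaccination status. If the vaccine effect is additive and the same in both cohorts,

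bias = [P(Cohort 1 | vaccinated) - P(Cohort 1 | unvaccinated)] x D.

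| Assumed coverage, Cohort 1 / Cohort 2 | Vaccinated (C1 + C2) | Unvaccinated (C1 + C2) | Bias |
|---|---|---|---|
| 70% / 70% | 35 + 21 | 15 + 9 | 0.625 - 0.625 = 0 |
| 60% / 80% | 30 + 24 | 20 + 6 | 0.556 - 0.769 = -0.21 D |
| 80% / 60% | 40 + 18 | 10 + 12 | 0.690 - 0.455 = +0.24 D |
| 50% / 90% | 25 + 27 | 25 + 3 | 0.481 - 0.893 = -0.41 D |
| 90% / 50% | 45 + 15 | 5 + 15 | 0.750 - 0.250 = +0.50 D |

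The bias can take either sign and vanishes at equal coverage.

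**3. Confounding versus mixing, on seropositivity.** Assume 20 of 50 (Cohort 1) and 21 of 30 (Cohort 2) are vaccinated, with seropositivity of 85% if vaccinated and, if unvaccinated, 40% in Cohort 1 and 5% in Cohort 2.

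- Unstratified: unvaccinated (30 x 0.40 + 9 x 0.05)/39 = 12.45/39 = 31.9%; difference 85 - 31.9 = 53.1 points.
- Within cohort: 85 - 40 = 45 (Cohort 1) and 85 - 5 = 80 (Cohort 2).
- Weighted 50:30: (45 x 50 + 80 x 30)/80 = 58.1. Confounding by cohort is 58.1 - 53.1 = about 5 points.
- With 20% in unvaccinated Cohort 1 women: 6.45/39 = 16.5%, difference 68.5; weighted (65 x 50 + 80 x 30)/80 = 70.6; confounding about 2 points.
- With the 40% and 5% rates and equal 70% coverage: (15 x 0.40 + 9 x 0.05)/24 = 26.9%, difference 58.1. This equals the weighted value, so confounding is zero, yet 58.1 describes neither cohort (45 and 80).
- With 30% instead of 5% in unvaccinated Cohort 2 women (borrowing the Section 2 figure for anogenital HPV, which is not serology) and the 20/50 and 21/30 coverage: (12 + 2.7)/39 = 37.7%, difference 47.3 against 55 within Cohort 2. If Cohort 1 is at 20%, (6 + 2.7)/39 = 22.3%, difference 62.7 against 55, and the order reverses.

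**4. Precision after stratifying.** Detectable difference in SD units = (1.96 + 0.84) x sqrt(1/n1 + 1/n2), for 80% power and two-sided 0.05 (both assumed), with equal coverage in the cohorts.

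| Assumed coverage | All women | Cohort 1 | Cohort 2 |
|---|---|---|---|
| 50% | 40 v 40: 0.63 | 25 v 25: 0.79 | 15 v 15: 1.02 |
| 70% | 56 v 24: 0.68 | 35 v 15: 0.86 | 21 v 9: 1.12 |
| 90% | 72 v 8: 1.04 | 45 v 5: 1.32 | 27 v 3: 1.70 |

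Stratified estimates with intervals are feasible. Tests within Cohort 2 would detect only large differences.

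**5. Who is in Cohort 2.** Section 4 defines it as women aged 18 or over who are not sexually active. Its criteria in Sections 5.2 and 5.3 require only PaHIV, female sex, age and capacity to consent. A sexually active pregnant woman, excluded from Cohort 1, would meet every listed criterion for Cohort 2.

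**The case against.** The strongest reply is that Section 9 commits to no faulty comparison. It promises a measurement of titres in vaccinated and unvaccinated women, and the comparison it names is with hepatitis B vaccination. A reader might infer a formal vaccinated-versus-unvaccinated test pooled over all 80 women; the text does not state one. The unspecified other correlates of titre could include sexual activity: Section 6.3 records coitarche, lifetime partners, STIs, genital warts and vaccination history, and Section 7.2 codes cohort into the sample number. These points stand, so separation is unspecified rather than ruled out. They do not remove the gap. Titres shown by vaccination status alone still present a contrast, and the listed tests, used unadjusted, cannot separate vaccination from sexual exposure.

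Two further inferences are tempting and unsupported. One is that Cohort 2 offers a clean, infection-free contrast. Section 2 cites 30% anogenital HPV in non-sexually active girls with PaHIV, and the listed criteria do not keep sexually active women out. The other is that the gap between 53 and 80 points in step 3 measures confounding. On those same assumptions only about 5 points do; the rest is a difference between cohorts.

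It is also fair that unequal coverage is conjecture. Section 2 describes a catch-up programme to age 18, and Section 4 says that vaccination is available to all women under 25. Coverage could be similar in the two cohorts.

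**Conclusion.** The concern holds in a limited form. Followed as written, Section 9 groups titres by vaccination status without separating the cohorts, so infection-derived and vaccine-derived antibody are mixed whenever the titres are read as vaccine response. Any confounding of the unstratified contrast is of unknown size and sign: zero for an additive titre shift at equal coverage, and between -0.41 D and +0.50 D over the coverages tried in step 2. At equal coverage, the unvaccinated reference group still mixes women with different exposure. All of these magnitudes rest on assumed coverage and seropositivity.

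Severity is minor to moderate. The serology is an exploratory secondary outcome, and the primary outcome is unaffected.

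**What to change.** In Section 9:

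- Report type-specific geometric mean titres with 95% intervals in four cells: Cohort 1 and Cohort 2, each vaccinated and unvaccinated at enrolment.
- Present the vaccinated-versus-unvaccinated difference (a ratio of geometric means) within each cohort, as a descriptive estimate with its interval and without a test.
- State that Cohort 2 is the group expected to be less affected by sexually acquired infection, not an infection-free group, and that the unstratified contrast will not be interpreted as vaccine response.
- Analyse the enrolment and Visit 3 samples of women vaccinated after enrolment as within-woman pairs, as a supporting estimate. Count each such woman once in the four-cell table, by her status at enrolment.

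Reconcile the Cohort 2 definition in Section 4 with the criteria in Sections 5.2 and 5.3, so that the stratum means what its label says.

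The cost is wording and one table. Cohort, vaccination history and sexual history are already collected. The downside is small cells and wide intervals, especially for unvaccinated Cohort 2 women: nine at an assumed 70% coverage and three at 90%.
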